5.1 Procedures by Study Day – Every 3-Week Dosing Schedule (Q3W)

The following procedures will be performed during the study. Regardless of dosing schedule, all patients will complete the same Screening procedures described in [Section 5.1.1](#), as well as the same procedures described for the End of Treatment (EOT; [Section 5.1.8](#)), 12-Week Follow-up Visit ([Section 5.1.9](#)) and Long-term Follow-up ([Section 5.1.10](#)).

Visit procedures described in [Section 5.1.2](#) – [Section 5.1.7](#) are for patients on the Q3W Schedule.

The Schedule of Procedures for the Q3W and QW dosing schedules are shown in [Table 1](#) and [Table 3](#), respectively, in [Appendix 13.1](#). Timings for sample collections for assessment of PK, ██████████ and other parameters for the Q3W dosing schedule are shown in [Table 2](#), and Cycle 1 and Cycle 2+ of the QW dosing schedule in [Table 4](#) and [Table 5](#), respectively, in [Appendix 13.1](#).

For QW dosing, most of the assessments will remain uniform with the Q3W dosing assessments, with the following exceptions:

- Study drug administration will occur at Days 1, 8, and 15
- The Q3W Day 19 assessments will be performed on Day 15 (concurrently with the 3rd QW dose) for the QW patients
 - Note: Bone marrow aspirate (BMA) or biopsy for QW patients is still performed at Day 19 ± 3 days but must be performed prior to the first dose of the next cycle.
- Pharmacokinetic and Pharmacodynamics, ADA, serum CD25 (sCD25), WBC population, cytokines, and additional renal function studies sampling schedule is adjusted according to the prescribed dosing schedule.

5.1.1 Screening Period (Day –28 to –1)

The following procedures will be performed within 28 days prior to the Day 1 visit of Cycle 1, unless otherwise specified:

- A signed and dated Institutional Review Board (IRB)/Independent Ethics Committee (IEC) approved informed consent form (ICF) is to be obtained prior to performing any study evaluations. Results (clinical laboratory, etc.) obtained prior to the date of informed consent, but within the allowed timeframe for Screening, may be used for determination of patient eligibility only if obtained as part of the patient's standard of care.
- Demographic characteristics.

- Medical history (to include a complete history of all surgeries, significant diagnoses, all cancer treatment [including surgery, radiation therapy, chemotherapy, etc.], and FLT3-ITD status, if available).
- Serum or urine β -HCG pregnancy testing (women of child-bearing potential only).
- Physical examination, including neurological examination and including whole-body skin assessment. Whole-body skin assessment does not have to be performed by a dermatologist. However, any unexplained lesion is to be referred to a dermatologist for further evaluation and skin biopsy, if clinically warranted. The examination must include a determination if the patient has had any infection. At the discretion of the investigator, evaluation of any reported infection must be conducted to rule out infection with a microorganism that may be associated with autoimmune or neurological disease(s) as specified in the exclusion criteria.
 - Neurological assessment (as part of the physical examination) including strength, sensation, and deep-tendon reflexes throughout; examination does not need to be conducted by neurologist unless there are abnormal findings not explained by previous medical history (e.g., a patient with left sided weakness known to be a result of a previous CVA would not need to see a neurologist as part of this study) and that could be linked to or may be an early indicator of polyradiculopathy/GBS, such as ascending (bilateral) sensory loss or motor weakness.
- Vital signs (arterial blood pressure, heart rate, respiratory rate, body temperature), height and weight measurements.
- ECOG performance status.
- Collection of information on disease related mutations, including FLT-3, if available.
- Bone marrow aspirate (or biopsy if aspirate unattainable):
 - Evaluation of CD25 expression on blast cells, assessed at an approved local clinical laboratory (see Inclusion Criterion 2, [Section 4.2.1](#)).
 - Confirmation of disease, as per the WHO classification of acute leukemias,³⁴ at an approved local clinical laboratory.
- [REDACTED]
- [REDACTED]

- Hematology, coagulation panel, biochemistry, and urinalysis parameters.
 - Patients with a WBC value >15,000 cells/ μ L may receive treatment with hydroxyurea and/or leukopheresis, to lower the WBC value to <15,000 cells/ μ L prior to Day 1, Cycle 1 dosing. Hydroxyurea may be used during the first cycle to control WBC count at Investigator discretion.
 - Collection of mononuclear cells (MNC) sample.
- 12-lead electrocardiogram (ECG).
- Collection of AE information.
- Collection of information on medications used (including prescription or over-the-counter medication, herbal or naturopathic products) within the 14 days prior to the Day 1 visit.

5.1.2 Day 1 (\pm 3 days) of Each Cycle

Day 1 of each cycle occurs on infusion day. The following procedures will be performed prior to ADCT-301 infusion at each cycle, unless otherwise specified. Timing for sample collections and procedures is provided in [Appendix 13.1](#).

- Serum or urine pregnancy test (women of child-bearing potential, Cycle 1 only) required if the screening pregnancy test was obtained >7 days prior to Day 1.
- Physical examination, including neurological examination and including whole-body skin assessment, unless a physical examination was performed within 3 days prior to Day 1. The examination must include a determination if the patient has had any infection. At the discretion of the investigator, evaluation of any reported infection must be conducted to rule out infection with a microorganism that may be associated with autoimmune or neurological disease(s) as specified in the exclusion criteria.
- On Day 1 of Cycle 1, vital signs are to be measured before the start of the infusion, every 30 minutes during the infusion, and at the end of infusion. If no clinically significant changes occur during this first infusion, vital sign measurements are to be obtained prior to infusion start and end of infusion for all subsequent infusions. For Cycles 1 and 2, patients will also have vital signs measured 1 hour after the end of infusion and at discharge.
Note: Timing of measurements is \pm approximately 5 minutes.
- Weight, unless an assessment was performed within 3 days prior to Day 1.
- ECOG performance status, unless an assessment was performed within 3 days prior to Day 1.
- Hematology, coagulation panel, and biochemistry parameters will be measured prior to dosing unless the last sample was collected:
 - <24 hours before the start of ADCT-301 infusion on Day 1 of Cycle 1, or
 - <72 hours before the start of ADCT-301 infusion on Day 1 of Cycle 2 and subsequent cycles.

- Sample collection for:
 - Additional renal function studies
 - UrinalysisPrior to dosing unless the last sample was collected.
 - <24 hours before the start of ADCT-301 infusion on Day 1 of Cycle 1, or
 - <72 hours before the start of ADCT-301 infusion on Day 1 of Cycle 2 and subsequent cycles.
- 12-lead ECG (Cycles 1 and 2), before the start of infusion, at end of infusion, and at 3 hours after the end of infusion ([Section 7.3.5](#)).
- Sample collection for central laboratory analysis of soluble CD25 and ADA (all cycles).
- Sample collection for central laboratory analysis of PK parameters for Q3W is before the start of the ADCT-301 infusion, at the end of the infusion, and at 1, 3, and 6 hours after the end of the ADCT-301 infusion (Cycles 1 and 2). In all subsequent cycles, samples will be collected before the start of the ADCT-301 infusion and at the end of the infusion.
- Sample collection and shipment for central laboratory analysis of peripheral WBC populations (Part 2).
- Sample collection for cytokine analysis before the start of the ADCT-301 infusion and at 6 hours after the end of the infusion in Cycles 1 and 2.
- Collection of AE information.
- Collection of concomitant medication information.
- Premedication administration, if applicable ([Section 6.2](#)).
- ADCT-301 administration.

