 - Grade 4 tumor lysis syndrome (Grade 3 TLS will not constitute DLT unless it leads to irreversible end-organ damage).
 - Grade 3 or higher AEs (including nausea, vomiting, diarrhea, and electrolyte imbalances lasting more than 48 hours despite optimal therapy; excluding all grades of alopecia).
 - Grade 3 or higher hypersensitivity reaction (regardless of premedication).
 - Grade 3 or higher skin ulceration.
 - Peripheral sensory or motor neuropathy \geq Grade 2.

The DLT observation period for dose-escalation will be 1 cycle. Patients who experience a DLT during Cycle 1 are to be permanently discontinued from the study.

Investigational Product, Dosage, and Mode of Administration:

ADCT-301 is a sterile formulation containing PBD-conjugated HuMax[®]-TAC (DAR \geq 1), HuMax[®]-TAC (DAR = 0), and SG3249. It is provided pre-formulated in 10-mL glass vials containing approximately 30 mg of ADCT-301 per vial (deliverable volume 5.4 mL at 6 mg/mL). The appropriate quantity of ADCT-301 will be diluted in 50 mL of 5% dextrose in water (D5W).

Patients will receive a 1-hour intravenous (IV) infusion of ADCT-301 on

Day 1 of Cycle 1. If ADCT-301 is well tolerated after the first infusion, the infusion duration may be shortened to 30 minutes for subsequent cycles for that patient, at the Investigator's discretion.

The investigational product administration schedule is as follows:

Every 3-Week Administration

Patients will be given ADCT-301 on Day 1 of each 3-week (21-day) treatment cycle.

Weekly Administration

Patients will be given ADCT-301 (weekly [QW]) on Days 1, 8, and 15 of each 3-week (21-day) treatment cycle.

A patient will maintain the same treatment schedule throughout the duration of the trial.

Once a patient achieves CR/CRi, frequency or dose may be adjusted by the DESC based on emerging safety, efficacy, and PK profile.

The trial will be continuously monitored for emerging safety, efficacy and/or PK profile, and the DESC will determine if it is appropriate to maintain a QW schedule, revert to an every 3-week (Q3W) schedule, or test other dosing regimens.

Dose-Escalation Design:

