5.1.7 Day 19 (± 3 days) of Each Cycle

NOTE: If the timing of the assessments required at the Day 1 visit for the next cycle coincides with the Day 19 visit, assessments that are included at both Day 19 and Day 1 are to be performed only once.

- Physical examination, including neurological examination and including whole-body skin assessment for Cycles 1 and 2. The examination must include a determination if the patient has had any infection. At the discretion of the investigator, evaluation of any reported infection must be conducted to rule out infection with a microorganism that may be associated with autoimmune or neurological disease(s) as specified in the exclusion criteria.
- Weight and vital signs measurements (Cycles 1 and 2).
- Hematology and biochemistry parameters.
- Urinalysis and sample collection for additional renal function studies.
- Sample collection for central laboratory analysis of PK (Cycles 1 and 2).
- Sample collection for central laboratory analysis of peripheral WBC populations (Part 2).
- Collection of AE information.

- Collection of concomitant medication information.

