6.4 Dose Delays and Modifications

Patients will receive the first 2 cycles, irrespective of blood count recovery. For patients achieving a CR/CRi, the subsequent cycle would be delayed until peripheral blood count recovery (absolute neutrophil count [ANC] $>0.5 \times 10^9/L$ and/or platelets $>50 \times 10^9/L$).

The Investigator should suspend ADCT-301 dosing for up to 21 days for any patient who experiences a protocol-defined DLT during any treatment cycle. At the discretion of the Investigator, the dose may also be delayed for up to 21 days for any toxicity that does not meet DLT criteria. Resumption of dosing with ADCT-301 after suspension is at the discretion of the Investigator, based on assessment of the patient's clinical condition and whether or not the patient is deriving potential clinical benefit from treatment with ADCT-301. Following recovery to CTCAE Grade 1 or to baseline grade, treatment with ADCT-301 may resume at the Investigator's discretion.

Patients who resume treatment following a dose delay may, at the discretion of the Investigator, have their dose reduced by 1 dose level. If toxicity recurs at a severity that would mandate a dose delay, then the dose may be further reduced 1 dose level. If toxicity recurs at such level, then the patient is to be discontinued from treatment. Dose re-escalation is allowed at the Investigator's discretion, at maximum to the dose level the patient was initially assigned to.

Dosing frequency may be adjusted according to individual patient response as described in [Section 4.1.1](#).

Patients experiencing certain types of infection during the course of participation in this clinical study also must delay further dosing, as stipulated in [Section 7.3.4.5](#).

Patients experiencing any autoimmune toxicities (e.g., endocrinopathies) \geq grade 1 need to be followed at least weekly to quickly detect deterioration and modify dosing as per DLT criteria (can be done by telephone unless symptoms worsen).

Patients who experience a DLT ([Section 7.3.1.1](#)) during Cycle 1 are to be permanently withdrawn from the study. Patients who experience the following significant toxicities will be immediately and permanently withdrawn from treatment with ADCT-301:

- Any patient who experiences a CTCAE Grade 3 or higher hypersensitivity reaction, regardless of premedication, during any cycle of treatment ([Appendix 13.2](#)).

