7.3.1 Dose-Limiting Toxicities and Dose-Escalation Scheme

7.3.1.1 Definition of Dose-Limiting Toxicities

A DLT is defined as any of the following events, except those that are clearly due to underlying disease or extraneous causes:

- A hematologic DLT is defined as:
 - Grade 3 or higher event of neutropenia and/or thrombocytopenia or a Grade 4 anemia, with a hypocellular bone marrow lasting for 6 weeks or more after the start of a cycle, in the absence of residual leukemia (i.e., with <5% blasts). In case of a normocellular bone marrow with <5% blasts, 8 weeks with \geq Grade 3 pancytopenia will be considered a DLT.
- A non-hematologic DLT is defined as:
 - Grade 4 tumor lysis syndrome (Grade 3 TLS will not constitute DLT unless it leads to irreversible end-organ damage).
 - Grade 3 or higher AEs (including nausea, vomiting, diarrhea, and electrolyte imbalances lasting more than 48 hours despite optimal therapy; excluding all grades of alopecia).
 - Grade 3 or higher hypersensitivity reaction (regardless of premedication).
 - Grade 3 or higher skin ulceration.
 - Peripheral sensory or motor neuropathy \geq Grade 2.

Note: The DLT observation period for dose-escalation will be 1 cycle. Patients who experience a DLT during Cycle 1 are to be permanently discontinued from the study.

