8.4 Analysis Sets

Six analysis sets will be used in this study:

- The Safety analysis set will consist of all patients who receive study drug.
- The DLT-evaluable analysis set will consist of all patients in Part 1 who receive study drug and excludes patients who discontinue from the study during the first 21-day cycle without experiencing a DLT.
- The Efficacy analysis set will consist of all patients with valid baseline data who receive at least 2 doses of study drug, or who have documented progression of disease at any time after the first dose of study drug.
- The PK analysis set will consist of all patients who receive study drug and have sufficient concentration data for PK analysis.
- The PD analysis set will consist of all patients who receive study drug and have sufficient data available for analysis.

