4.2 Subject Disposition

For the Safety analysis set, the number and percentage of subjects who discontinued study treatment and discontinued the study for each reason will be tabulated for each dose level.

Subject disposition data will be listed.

The number and percentage of patients with any important clinical study report (CSR) reportable protocol deviation will be summarized overall and by type of deviation. The pre-defined important CSR reportable protocol deviations are listed below; in addition, any other protocol deviations deemed by ADCT medical to be important CSR reportable deviations will be included in the summary.

1. Patient entered the study even though they did not satisfy the entry criteria
2. Patient received an excluded concomitant treatment
3. Patients who developed withdrawal criteria during the study but were not withdrawn.
The withdrawal criteria include:
 - Grade 3 or higher hypersensitivity reaction
 - a recurrent Grade 3 or 4 toxicity, excluding hematological toxicity
 - a protocol-defined dose-limiting toxicity (DLT) during Cycle 1

- a dosing delay >21 (except in case of potential patient benefit, which must be approved by the Sponsor) or
 - diagnosis of polyradiculopathy/GBS with the level 1 of diagnostic certainty
 - Grade ≥ 3 neurologic toxicities, defined as peripheral sensory and peripherally motor neuropathies
4. toxicity recurs at the 2nd reduced dose level and at a severity that would mandate a treatment withdrawal Patient who received the wrong treatment or incorrect dose. For example,
- actual dose of study drug was more than 15% greater than protocol defined planned dose level
 - patient started next cycle less than 18 days later after Day 1 of the most recent treatment cycle

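### For Part 1 patients dosed every 3 weeks, the ±3-day window on Day 1 permits the Cycle 2 infusion on Day 19, up to 3 days before the 21-day DLT cycle is complete

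*Protocol*

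**What the plan says.** - **Cycle length.** The protocol synopsis, under every-3-week administration, states: "Patients will be given ADCT-301 on Day 1 of each 3-week (21-day) treatment cycle".
- **Window on the dose.** The heading of Protocol 5.1.2 puts ±3 days on Day 1 of each cycle, and its text begins: "Day 1 of each cycle occurs on infusion day. The following procedures will be performed prior to ADCT-301 infusion at each cycle". The window therefore moves the infusion as well as the assessments. Protocol 5.1 says that the visit sections 5.1.2 to 5.1.7 "are for patients on the Q3W Schedule".
- **DLT period.** Protocol 7.3.1.1: "The DLT observation period for dose-escalation will be 1 cycle. Patients who experience a DLT during Cycle 1 are to be permanently discontinued". The DLT-evaluable set in 8.4 "excludes patients who discontinue from the study during the first 21-day cycle without experiencing a DLT".
- **Action on a DLT.** Protocol 6.4: "The Investigator should suspend ADCT-301 dosing for up to 21 days for any patient who experiences a protocol-defined DLT during any treatment cycle". The same section lets the investigator delay a dose for lesser toxicity.
- **Deviation limit.** SAP 4.2 gives as an example of an important dosing deviation: "patient started next cycle less than 18 days later after Day 1 of the most recent treatment cycle".

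No visible text in either document requires 21 days to pass before the Cycle 2 dose. The schedule tables in Appendix 13.1 are not shown.

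**The concern.** A patient with a Cycle 1 DLT is meant to receive no more drug. That works for Q3W patients only if the observation period closes before the second infusion. The Day 1 window lets the infusion come first, and the SAP limit is set where the earliest such infusion goes unreported. If a DLT then appears on or before Day 21, the patient has had a dose that the discontinuation rule was meant to prevent. Neuropathy of Grade 2 or higher is a DLT, and Amendment 5 was written because of Guillain-Barré syndrome and polyradiculopathy, so a second dose given shortly before late signs appear is not trivial for that patient.

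**Working it through.** **Day count, starting with the SAP figure.** Inputs: cycle of 21 days (synopsis), window of 3 days (5.1.2), Cycle 1 infusion on Day 1.

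- Nominal Cycle 2 Day 1 = 1 + 21 = Day 22.
- Earliest Cycle 2 infusion = 22 − 3 = Day 19.
- Interval = 21 − 3 = 18 days. This matches the SAP 4.2 limit exactly. A start at 18 days is not less than 18 days, so it is not flagged.
- Days observed before the second dose = 18 of 21 (85.7%). Days 19, 20 and 21 fall on or after it.
- With a 0/+3-day window the earliest infusion is Day 22, and all 21 days come first.

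**Which patients are exposed.** A DLT already evident at the pre-dose visit should stop the infusion. Section 5.1.2 schedules a physical and neurological examination, laboratory tests and AE collection beforehand, and 6.4 suspends dosing. An examination from the previous 3 days, or Cycle 2 blood tests from less than 72 hours earlier, may be reused, but AE collection carries no such exemption. This leaves early-dosed patients whose DLT is first evident after the infusion and by Day 21.

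**Illustrative size.** The documents give no DLT rate, DLT timing or frequency of early dosing, so all three are assumed. Let p be the 21-day DLT probability, with constant hazard over 21 days and no added hazard from dose 2. Let d be the Cycle 2 infusion day and f the fraction of patients dosed on that day. Any DLT arising before Day d is taken as caught.

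- Probability that a DLT falls from Day d to Day 21: w = p − [1 − (1 − p)^((d−1)/21)].
- Chance that at least 1 of 3 patients is re-dosed before the DLT appears: 1 − (1 − f·w)³.

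For p = 0.25 and d = 19: w = 0.25 − [1 − 0.75^(18/21)] = 0.0315. With f = 0.5, 1 − (1 − 0.0157)³ = 4.6%.

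| p | d | w | f = 20% | f = 50% | f = 100% |
|---|---|---|---|---|---|
| 0.20 | 19 | 0.0259 | 1.5% | 3.8% | 7.6% |
| 0.25 | 19 | 0.0315 | 1.9% | 4.6% | 9.1% |
| 0.33 | 19 | 0.0395 | 2.3% | 5.8% | 11.4% |
| 0.25 | 20 | 0.0208 | 1.2% | 3.1% | 6.1% |
| 0.25 | 21 | 0.0103 | 0.6% | 1.5% | 3.1% |

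The last column needs every patient dosed early and is an upper bound. All figures shrink if DLTs cluster early in the cycle.

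**The case against.** **Weekly patients are dosed on Days 8 and 15 of Cycle 1, inside the same DLT period.** True, so re-dosing during observation is not foreign to this protocol. But that is the planned weekly regimen. It gives no reason for a Q3W patient to receive the second cycle early through a scheduling window.

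**The pre-dose checks cover most of the risk.** This stands, and it is why the point concerns only DLTs not yet evident at the infusion.

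**The practical reach is small.** This also stands. Protocol 4.1.1 limits remaining escalation under Amendment 5 to 9 patients unless 2 more respond, and gives the maximum as a weekly dose, although the steering committee may return to Q3W. SAP 3.3 records that the trial ended before escalation was complete. The SAP keeps only a safety set and lists DLTs (SAP 4.1 and the section on dose-limiting toxicities). A footnote in the unseen Appendix 13.1 tables cannot be ruled out.

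**Stronger readings that a reader might draw.**

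- *The DLT window shrinks to 18 days and the 3+3 rule is biased.* This needs the one-cycle period to end at an early infusion. No passage says so, and the synopsis and 8.4 both state a 21-day cycle. If events on Days 19 to 21 were discarded, the chance of clearing a level at p = 0.25 would rise from 60.0% to at most 66.8%, but the documents do not support discarding them.
- *Section 5.1.7 foresees early dosing.* Its note begins "If the timing of the assessments required at the Day 1 visit for the next cycle coincides with the Day 19 visit". Day 19 plus 3 is Day 22, the on-time date, so punctual dosing explains the note.
- *The SAP authorizes a Day 19 dose.* Its 18-day line is an example in a list of reportable deviations. It is consistent with the window, but the permission comes from 5.1.2.

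**Conclusion.** The point holds in limited form. On the visible text, a Part 1 Q3W patient may receive Cycle 2 up to 3 days before the 21-day DLT cycle is complete, and the SAP would not report it. The main effect is one avoidable dose in a patient who should have been discontinued. Since the event should still count as a Cycle 1 DLT, an effect on MTD determination is not shown.

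The day count rests on the documents alone. The illustrated chances rest wholly on the assumed DLT probability, constant hazard and early-dosing fraction. Severity is minor: the change is worth making to the protocol as written, but since the trial has stopped in Part 1 it can now alter only how early Cycle 2 starts are reported, not patient exposure.

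**What to change.** 1. Protocol 5.1.2: for Part 1 Q3W patients, set the Cycle 2 Day 1 window to 0/+3 days, so the infusion is not given before Day 22. Later cycles can keep ±3 days.
2. SAP 4.2: for the same patients, flag a Cycle 2 start less than 21 days after Cycle 1 Day 1.
3. If the DLT period is restated, say that an event on Days 1 to 21 counts as a Cycle 1 DLT even when Cycle 2 was given early. Leave the 6- and 8-week hematologic criteria in 7.3.1.1 unchanged, because they cannot be met within 21 days.

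Cost: up to 3 days less scheduling freedom for one infusion per patient, and short wording changes in the protocol and SAP.
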